## GI Adverse Event Management Algorithm

Rule out non-inflammatory causes. If non-inflammatory cause is identified, treat accordingly and continue I-O therapy.  
Opiates/narcotics may mask symptoms of perforation. Infliximab should not be used in cases of perforation or sepsis.

[figure not shown]
Patients on IV steroids may be switched to an equivalent dose of oral corticosteroids (eg, prednisone) at start of tapering or earlier, after sustained clinical improvement is observed. Lower bioavailability of oral corticosteroids should be taken into account when switching to the equivalent dose of oral corticosteroids.

\* Discontinue for Grade 4 diarrhea or colitis. For Grade 3 diarrhea or colitis, 1) Nivolumab monotherapy: Nivolumab can be delayed. 2) Nivolumab+ Ipilimumab combination: Ipilimumab should be discontinued while nivolumab can be delayed. Nivolumab monotherapy can be resumed when symptoms improve to Grade 1. Please refer to protocol for dose delay and discontinue criteria for other combinations.

28-Sep-2020

## Renal Adverse Event Management Algorithm

Rule out non-inflammatory causes. If non-inflammatory cause, treat accordingly and continue I-O therapy.

[figure not shown]
Patients on IV steroids may be switched to an equivalent dose of oral corticosteroids (eg, prednisone) at start of tapering or earlier, after sustained clinical improvement is observed. Lower bioavailability of oral corticosteroids should be taken into account when switching to the equivalent dose of oral corticosteroids.

28-Sep-2020

## Pulmonary Adverse Event Management Algorithm

Rule out non-inflammatory causes. If non-inflammatory cause, treat accordingly and continue I-O therapy.  
Evaluate with imaging and pulmonary consultation.

[figure not shown]

Patients on IV steroids may be switched to an equivalent dose of oral corticosteroids (eg, prednisone) at start of tapering or earlier, after sustained clinical improvement is observed. Lower bioavailability of oral corticosteroids should be taken into account when switching to the equivalent dose of oral corticosteroids.

28-Sep-2020

## Hepatic Adverse Event Management Algorithm

Rule out non-inflammatory causes. If non-inflammatory cause, treat accordingly and continue I-O therapy.  
Consider imaging for obstruction.

Patients on IV steroids may be switched to an equivalent dose of oral corticosteroids (e.g. prednisone) at start of tapering or earlier, after sustained clinical improvement is observed. Lower bioavailability of oral corticosteroids should be taken into account when switching to the equivalent dose of oral corticosteroids.

[figure not shown]
Λ Please refer to protocol dose delay and discontinue criteria for specific details.

\*The recommended starting dose for AST or ALT > 20 x ULN or bilirubin >10 x ULN is 2 mg/kg/day methylprednisolone IV.

28-Sep-2020

## Endocrinopathy Adverse Event Management Algorithm

Rule out non-inflammatory causes. If non-inflammatory cause, treat accordingly and continue I-O therapy.  
Consider visual field testing, endocrinology consultation, and imaging.

[figure not shown]
Patients on IV steroids may be switched to an equivalent dose of oral corticosteroids (eg, prednisone) at start of tapering or earlier, after sustained clinical improvement is observed. Lower bioavailability of oral corticosteroids should be taken into account when switching to the equivalent dose of oral corticosteroids.

28-Sep-2020

## Skin Adverse Event Management Algorithm

Rule out non-inflammatory causes. If non-inflammatory cause, treat accordingly and continue I-O therapy.

Patients on IV steroids may be switched to an equivalent dose of oral corticosteroids (e.g. prednisone) at start of tapering or earlier, after sustained clinical improvement is observed. Lower bioavailability of oral corticosteroids should be taken into account when switching to the equivalent dose of oral corticosteroids.

[figure not shown]
\*Refer to NCI CTCAE v5 for term-specific grading criteria.

^If Steven-Johnson Syndrome (SJS), toxic epidermal necrosis (TEN), Drug Reaction with Eosinophilia and Systemic Symptoms (DRESS) is suspected, withhold I-O therapy and refer patient for specialized care for assessment and treatment. If SJS, TEN, or DRESS is diagnosed, permanently discontinue I-O therapy.

28-Sep-2020

# Neurological Adverse Event Management Algorithm

Rule out non-inflammatory causes. If non-inflammatory cause, treat accordingly and continue I-O therapy.

[figure not shown]

Patients on IV steroids may be switched to an equivalent dose of oral corticosteroids (eg. prednisone) at start of tapering or earlier, after sustained clinical improvement is observed. Lower bioavailability of oral corticosteroids should be taken into account when switching to the equivalent dose of oral corticosteroids.

^Discontinue for any grade myasthenia gravis, Guillain-Barre syndrome, treatment-related myelitis, or encephalitis.

28-Sep-2020

## Myocarditis Adverse Event Management Algorithm

For the protocols under CTCAE version 5.0. Patients on IV steroids may be switched to an equivalent dose of oral corticosteroids (eg, prednisone) at start of tapering or earlier, once sustained clinical improvement is observed. Lower bioavailability of oral corticosteroids should be taken into account when switching to the equivalent dose of oral corticosteroids. Prophylactic antibiotics should be considered in the setting of ongoing immunosuppression.

ATG = anti-thymocyte globulin; BNP = B-type natriuretic peptide; ECG = electrocardiogram; IV = intravenous; MRI = magnetic resonance imaging

[figure not shown]
11-Sep-2020

Protocol Amendment No.: 07  
Date: 04-Jan-2023

Approved v1000 930122012 10.0

## APPENDIX 6 ECOG PERFORMANCE STATUS

PERFORMANCE STATUS CRITERIA: ECOG Score	
ECOG (Zubrod)	
Score	Description
0	Fully active; able to carry on all pre-disease performance without restriction
1	Restricted in physically strenuous activity but ambulatory and able to carry out work of a light or sedentary nature, e.g., light house work, office work.
2	Ambulatory and capable of all self care but unable to carry out any work activities; up and about more than 50% of waking hours.
3	Capable of only limited self care; confined to bed or chair more than 50% of waking hours.
4	Completely disabled; cannot carry on any self care; totally confined to bed or chair.
5	Dead

## **APPENDIX 11      RESPONSE EVALUATION CRITERIA IN SOLID TUMORS GUIDELINES (VERSION 1.1) WITH BMS MODIFICATIONS**

### **1                    EVALUATION OF LESIONS**

Solid tumors will be evaluated using Response Evaluation Criteria In Solid Tumors version 1.1 (RECIST 1.1) guideline with BMS modifications.

At baseline, tumor lesions/lymph nodes will be categorized as measurable or non-measurable as follows:

#### **1.1                Measurable**

**Tumor lesions:** Must be accurately measured in at least one dimension (longest diameter in the plane of measurement is to be recorded) with a minimum size of:

10 mm by CT/MRI scan (scan slice thickness no greater than 5 mm), or  $\geq 2 \times$  slice thickness if greater than 5mm.

**Malignant lymph nodes:** To be considered pathologically enlarged and measurable, a lymph node must be  $\geq 15$  mm in short axis when assessed by CT/MRI scan (scan slice thickness recommended to be no greater than 5 mm).

Lymph nodes merit special mention since they are normal anatomical structures which may be visible by imaging even if not involved by tumor. Pathological nodes which are defined as measurable and may be identified as target lesions must meet the criterion of a short axis of  $\geq 15$  mm by CT/MRI scan. Only the short axis of these nodes will contribute to the baseline sum. The short axis of the node is the diameter normally used by radiologists to judge if a node is involved by solid tumor. Nodal size is normally reported as two dimensions in the plane in which the image is obtained (for CT scan this is almost always the axial plane; for MRI the plane of acquisition may be axial, sagittal or coronal). The smaller of these measures is the short axis. For example, an abdominal node which is reported as being 20 mm x 30 mm has a short axis of 20 mm and qualifies as a malignant, measurable node. In this example, 20 mm should be recorded as the node measurement. All other pathological nodes (those with short axis  $\geq 10$  mm but  $< 15$  mm) should be considered non-target lesions. Nodes that have a short axis  $< 10$  mm are considered non-pathological and should not be recorded or followed.

Note: Lesions on X-Ray are not to be selected as Target or Non-Target Lesions.

#### **1.2                Non-Measurable**

All other lesions are considered non-measurable, including small lesions (longest diameter  $< 10$  mm or pathological lymph nodes with  $\geq 10$  to  $< 15$  mm short axis) as well as truly non-measurable lesions. Lesions considered truly non-measurable include: leptomeningeal disease, inflammatory breast disease, lymphangitic involvement of skin or lung, abdominal masses/abdominal organomegaly identified by physical exam that is not measurable by reproducible imaging techniques.

Note: Lesions on X-Ray are not to be selected as Target or Non-Target Lesions.

### 1.3 Special considerations regarding lesion measurability

#### 1.3.1 Bone lesions

- Bone scan, PET scan and plain films are **not** considered adequate imaging techniques to measure bone lesions. However, these techniques can be used to confirm the presence or disappearance of bone lesions.
- Lytic bone lesions or mixed lytic-blastic lesions, with *identifiable soft tissue components*, that can be evaluated by cross sectional imaging techniques such as CT or MRI can be considered as measurable lesions if the *soft tissue component* meets the definition of measurability described above.
- Blastic bone lesions are non-measurable.

### 1.4 Baseline DOCUMENTATION OF ‘TARGET’ AND ‘NON-TARGET’ LESIONS

When more than one measurable lesion is present at baseline all lesions up to a maximum of five lesions total (and a maximum of two lesions per organ) representative of all involved organs should be identified as target lesions and will be recorded and measured at baseline (this means in instances where patients have only one or two organ sites involved a maximum of two and four lesions respectively will be recorded).

Note: A maximum of two lesions can be selected per organ system. For example, a maximum of two lung lesions can be selected (selected from one lung or one lesion from each). A maximum of two lymph nodes can be selected at baseline, as the lymphatic system is considered one organ.

Target lesions should be selected on the basis of their size (lesions with the longest diameter), be representative of all involved organs, but in addition should be those that lend themselves to reproducible repeated measurements. It may be the case that, on occasion, the largest lesion does not lend itself to reproducible measurement in which circumstance the next largest lesion which can be measured reproducibly should be selected.

A sum of the diameters (longest for non-nodal lesions, short axis for nodal lesions) for all target lesions will be calculated and reported as the baseline sum diameters. If lymph nodes are to be included in the sum, then as noted above, only the short axis is added into the sum. The baseline sum diameters will be used as reference to further characterize any objective tumor regression in the measurable dimension of the disease.

All other lesions (or sites of disease) including pathological lymph nodes should be identified as non-target lesions and should also be recorded at baseline. Measurements are not required and these lesions should be followed as ‘present’, ‘absent’, or in rare cases ‘unequivocal progression’ (more details to follow). In addition, it is possible to record multiple non-target lesions involving the same organ as a single item on the case record form (eg, ‘multiple enlarged pelvic lymph nodes’ or ‘multiple liver metastases’).

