**Table 2-1: Screening Procedural Outline for All Study Parts (CA224048)**

Procedure	Screening Visit -28 days	Day -14 to Day -1 Visit	Notes a
Adverse Event Reporting			
Monitor for Serious Adverse Events (SAEs)	X		All SAEs must be collected from the date of participant's written consent until [REDACTED] after discontinuation of dose administration or participation in the study if the last scheduled visit occurs at a later time. [REDACTED] Electronic SAEs (eSAEs) should be approved in the BMS Electronic Data Capture (EDC) tool within 5 business days of entry.
Clinical Complaints		X	Collected during the 2 weeks prior to Cycle 1 Day 1.
Tumor Assessments/Baseline Efficacy Assessments			
Body Imaging	X		See Section 9.1 ; must be performed within 28 days prior to first dose.
Brain Imaging	X		Magnetic resonance imaging (MRI) of the brain without and with contrast is required for participants with known or suspected brain metastases who have not had brain imaging within [REDACTED] of anticipated first study drug administration. See imaging assessment details in Section 9.1 .
Other Imaging: Bone Scan	X		See Section 9.1 ; as clinically indicated per local standards.

Abbreviations: AE = adverse events; [REDACTED]; CRF = case report form; [REDACTED]; ECOG = Eastern Cooperative Oncology Group; EDC = electronic data capture; [REDACTED]; eSAEs = electronic serious adverse events; FSH = follicle stimulating hormone; G6PD = glucose-6-phosphate dehydrogenase; HIV = human immunodeficiency virus; IgG = immunoglobulin; IRT = interactive response technology; [REDACTED]; MRI = magnetic resonance imaging; [REDACTED]; PE = physical examination; [REDACTED]; SAE = serious adverse events; [REDACTED]; WOCBP = women of childbearing potential.

a Some of the assessments referred to in this section may not be captured as data in the case report form (CRF). They are intended to be used as safety monitoring by the treating physician. Additional testing or assessments may be performed as clinically necessary or where required by institutional or local regulations.

**Table 2-2: On-treatment Procedural Outline Part 1A (Relatlimab + Nivolumab + BMS-986205) and Part 1B (Relatlimab + Nivolumab + Ipilimumab)**

Procedure	Cycle 1 [REDACTED]					Cycle 2+[REDACTED]						Notes e,f

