## 2) Type of Participant and Target Disease Characteristics

- a) Histologic or cytologic confirmation of an incurable solid malignancy that is advanced (metastatic and/or unresectable), with measurable disease per RECIST v1.1.

i)

- b) Presence of at least 1 lesion with measurable disease as defined by RECIST v1.1 criteria for response assessment. Participants with lesions in a previously irradiated field as the sole site of measurable disease will be permitted to enroll provided that the lesion(s) have demonstrated clear progression prior to the time of informed consent and can be measured accurately.
- c) Documentation of IO-containing therapy should include start, stop, and progression dates of prior IO therapy.
- d) Eastern Cooperative Oncology Group Performance Status (ECOG) status of 0 or 1 (see [Appendix 6](#)).
- e) Life expectancy  $\geq 12$  weeks at the time of informed consent per Investigator assessment.

f)

- g) Ability to comply with scheduled visits, treatment schedule, laboratory testing, and other requirements of the study (for example, PK, and PD sample collection and required study follow-up).

- h) Participants receiving BMS-986205: Availability of a suitable formulation and mode of administration for the participant's needs, as detailed in the IB and Pharmacy Manual at the time of enrollment **Note:** *at the time of original protocol finalization, BMS-986205 is available in a tablet formulation only and participants should be able to swallow intact tablets to enroll on the study. Ongoing clinical pharmacology studies have expanded the options available. Full details can be found in the IB and Pharmacy Manual, which will be updated throughout the study. Please contact the Medical Monitor with any queries.*

i)

[REDACTED]

[REDACTED] Participants who refuse potentially curative salvage surgery for recurrent disease are ineligible. Participants must have tumor progression or recurrence after prior platinum-containing systemic therapy for recurrent or metastatic disease. In addition, participants who have progressed within 6 months of platinum-based therapy used as part of concurrent chemoradiation (definitive or adjuvant therapy) are also eligible. Clinical progression is defined as progression of a lesion at least 10 mm in size that is amenable to caliper measurement (eg, superficial skin lesion per RECIST v1.1) or a lesion that has been visualized and photographically recorded with measurements and shown to have progressed.

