## 6.2 Exclusion Criteria

### 1) Medical Conditions

- a) Participants with known or suspected central nervous system (CNS) metastases or with the CNS as the only site of active disease are excluded with the following exceptions:
  - i) Participants with controlled brain metastases will be allowed to enroll. Controlled brain metastases are defined as those with no radiographic progression for at least 4 weeks after radiation and/or surgical treatment at the time of consent. Participants must have been off of steroids for at least 2 weeks prior to informed consent, and have no new or progressive neurological signs and symptoms.
  - ii) Participants with signs or symptoms of brain metastases are not eligible unless brain metastases are ruled out by computed tomography (CT) or magnetic resonance imaging (MRI).
- b) Participants with a history of interstitial lung disease/pneumonitis.
- c) For participants to be treated with BMS-986205: [REDACTED]

- d) For participants to be treated with BMS-986205: [REDACTED]
- e) For participants to be treated with BMS-986205: [REDACTED]
- f) Concurrent malignancy (present during screening) requiring treatment or history of prior malignancy active within 2 years prior to treatment assignment (ie, participants with a history of prior malignancy are eligible if treatment was completed at least 2 years before treatment assignment and the participant has no evidence of disease). Participants with history of prior early stage basal/squamous cell skin cancer or non-invasive or in situ cancers that have undergone definitive treatment at any time are also eligible.
- g) Participants with an active, known, or suspected autoimmune disease; however, participants with type I diabetes mellitus, hypothyroidism only requiring hormone replacement, skin disorders (such as vitiligo, psoriasis, or alopecia) not requiring systemic treatment, or conditions not expected to recur in the absence of an external trigger, are permitted to enroll.
- h) Requirement for daily supplemental oxygen.
- i) Uncontrolled or significant cardiovascular disease including, but not limited to, any of the following:
  - i) Myocardial infarction (MI) or stroke/transient ischemic attack within the 6 months prior to consent.
  - ii) Uncontrolled angina within the 3 months prior to consent.
  - iii) Any history of clinically significant arrhythmias (eg, ventricular tachycardia, poorly controlled atrial fibrillation ventricular fibrillation, torsades de pointes).

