## 2) Prior/Concomitant Therapy

- a) Any of the following procedures or medications within 2 weeks prior to time of study drug administration:
  - i) Systemic or topical corticosteroids at immunosuppressive doses ( $>10$  mg/day of prednisone or equivalent) are NOT permitted. Inhaled or topical steroids, and adrenal replacement steroid doses  $> 10$  mg daily prednisone equivalent, **are** permitted in the absence of active autoimmune disease.
  - ii) Palliative radiation or gamma knife radiosurgery. Participants must have recovered (ie, Grade  $\leq 1$  or at baseline) from radiation-related toxicities prior to first study treatment.
  - iii) Treatment with complementary medications (eg, herbal supplements or traditional Chinese medicines) to treat the disease under study within 2 weeks prior to first study treatment. Such medications are permitted if they are used as supportive care. Refer to [Section 7.7.1](#) for prohibited/restricted therapies. Note: Prior traditional Chinese medicines with anticancer claims are not considered as a prior line of therapy.
- b) Any of the following procedures or medications within 4 weeks prior to study drug administration:
  - i) Any investigational cytotoxic drug. Exposure to any non-cytotoxic drug within 4 weeks or 5 half-lives (whichever is shorter) is prohibited. If 5 half-lives are shorter than 4 weeks, agreement with Sponsor/Medical Monitor is mandatory.
  - ii) Growth factors (eg, granulocyte-colony stimulating factor, granulocyte macrophage-colony stimulating factor, erythropoietin).
  - iii) Major surgery.

- c) Any of the following procedures or medications within 4 weeks prior to study drug administration:
  - i) Treatment with any live/attenuated vaccine within [REDACTED] of first study treatment, during treatment, and up to [REDACTED] post last dose.
  - ii) Allergen hyposensitization therapy.
- d) Inability to comply with restrictions and prohibited treatments as listed in [Section 7.7](#) Concomitant Therapy.
- e) Participation in any prior clinical study with nivolumab and/or ipilimumab, including participants in comparator arms, in which OS is listed as the primary or coprimary endpoint and which has not completed analysis based on the primary endpoint.
- f) Prior treatment with LAG-3 or IDO targeted agents.

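### Appendix 11 does not bar an irradiated lesion that has not since progressed from being a target when other measurable disease exists, and a target can be irradiated after its baseline scan until about Day -15

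*Combined protocol and SAP*

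**What the plan says.** - **Choice of targets.** Protocol Appendix 11, section 1.4: "Target lesions should be selected on the basis of their size (lesions with the longest diameter), be representative of all involved organs". The section adds that lesions must be measurable reproducibly, with at most five in total and two per organ. Section 1.3, on special considerations, deals with bone lesions only. Neither section mentions irradiated lesions.
- **Eligibility.** Section 6.1, criterion 2(b): "Participants with lesions in a previously irradiated field as the sole site of measurable disease will be permitted to enroll", on condition that the lesions "have demonstrated clear progression prior to the time of informed consent and can be measured accurately".
- **Baseline scan.** Table 2-1, Body Imaging: "must be performed within 28 days prior to first dose". Section 9 lets routine procedures done before consent serve as baseline if they fall within the window.
- **Radiation before dosing.** Section 6.2, criterion 2(a) excludes "Any of the following procedures or medications within 2 weeks prior to time of study drug administration", and item ii lists "Palliative radiation or gamma knife radiosurgery". That item also requires recovery from radiation toxicity, which is not a rule on measurement.
- **Response.** Appendix 11, section 2.1 defines PR as a fall of at least 30% from the baseline sum. Table 10.3.1-1 starts the best-response window at first dose and closes it at progression or subsequent therapy. PFS is censored at the last evaluable assessment before subsequent therapy, which includes tumor-directed radiotherapy.

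**The concern.** ORR, DCR and mDOR are primary endpoints (Table 4-1). The Part 2 cohorts have no comparator without a triplet, and a Simon two-stage design guides many of them, so single responses carry weight. If radiotherapy shrinks a target lesion after its baseline diameter was recorded, that shrinkage enters the same sum as any drug effect and cannot be separated from it. Confirmation at 28 days or later does not remove it if the shrinkage lasts.

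The protocol accepts the principle elsewhere. It stops counting best response at subsequent therapy, censors PFS for later radiotherapy, and asks for progression in the sole-site case. Radiotherapy shortly before the first dose confounds in the same way, but falls outside the best-response and PFS rules because those concern subsequent therapy only.

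**Working it through.** **1. Which rule covers which case**

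| Lesion irradiated | Other measurable disease | Visible rule | Can it be a target? |
|---|---|---|---|
| Before baseline scan | No | Inclusion 2(b): progression before consent | Yes, if progressed; order of radiation and progression not stated |
| Before baseline scan | Yes | None | Yes, progressed or not |
| After baseline scan, to about Day -15 | Yes | None | Yes, with a pre-radiation diameter |
| Last 2 weeks before dose | Either | Exclusion 2(a)(ii) | Participant excluded (palliative radiation, gamma knife) |

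**2. Length of the open window**

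Imaging window minus radiation exclusion window: 28 - 14 = 14 days, about Day -28 to Day -15. No visible text asks for a new baseline scan after radiation. Because routine scans may serve as baseline, the scan that prompts palliative radiation can itself be the baseline scan.

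**3. Shrinkage of one irradiated target that alone gives PR**

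If the lesion makes up share s of the baseline sum and nothing else changes, the shrinkage needed is 0.30 / s:

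- s = 1: 30%
- s = 2/3: 45%
- s = 0.5: 60%
- s = 0.4: 75%
- s = 0.3: 100%

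Two examples with assumed diameters:

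- Targets 40 + 20 mm, the irradiated one falling from 40 to 22 mm: sum 60 to 42 mm, (60 - 42)/60 = 30%, a PR.
- Targets 40 + 30 mm, the irradiated one falling 60% to 16 mm: sum 70 to 46 mm, 46/70 - 1 = -34.3%, a PR.

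**4. The opposite direction**

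- Lesion irradiated before the baseline scan and inert afterwards: 40 mm unchanged, the other lesion falling 60% from 30 to 12 mm. Sum 70 to 52 mm, 52/70 - 1 = -25.7%. This is SD, although the untreated lesion shrank well past 30%.
- PD is judged from the smallest sum. With a nadir of 46 mm, PD on target lesions needs 46 x 1.2 = 55.2 mm (a rise of 9.2 mm, above the 5 mm minimum). With a nadir of 70 mm it needs 70 x 1.2 = 84 mm. A lower nadir can therefore bring PD forward and shorten DOR and PFS.

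**5. Illustrative effect on ORR in the scan-then-irradiate sequence**

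Observed ORR = ORR + (1 - ORR) x f x q, where f is the share of participants with such a target and q the share of their non-responders turned into responders. Neither is in the documents. With an assumed true ORR of 20%:

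| f | q = 0.25 | q = 1 |
|---|---|---|
| 2% | 20.4% | 21.6% |
| 5% | 21.0% | 24.0% |
| 10% | 22.0% | 28.0% |

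For example, 0.20 + 0.80 x 0.02 x 0.25 = 0.204, and 0.20 + 0.80 x 0.10 x 1 = 0.28.

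**The case against.** The strongest reply is that the protocol already limits the problem and that we do not see all of it. Criterion 2(b) covers the case with most at stake, where the irradiated lesion is the only measurable disease. Criterion 2(a)(ii) closes the last 2 weeks. Appendix 11 rests on RECIST v1.1 with sponsor modifications, and that guideline is not in the file. Parts of section 6.1 and of the imaging text are blacked out, and the Imaging Manual is not provided. A rule may stand in any of these. This lowers confidence. It does not close the gap, because the target-selection section of Appendix 11 shows no redaction and is where such a rule belongs.

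The reply is also right on size. Cohort sizes and the frequency of recently irradiated targets are not visible, an irradiated lesion that is 30% of the sum must vanish to give PR by itself, and new lesions or non-target progression still give PD.

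Three stronger readings are tempting, and the documents do not support them:

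- A reader might infer that nothing prevents irradiation of a target right up to Day 1. Exclusion 2(a)(ii) contradicts that for palliative radiation and gamma knife.
- A reader might infer that the bias always inflates efficacy. Step 4 of the working shows that it need not.
- A reader might add treated brain metastases as a further case of irradiation after the baseline scan. Exclusion 1(a) requires "no radiographic progression for at least 4 weeks after radiation and/or surgical treatment at the time of consent". Radiation then precedes first dose by at least 4 weeks, while the scan falls within the last 28 days, so that sequence does not arise.

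**Conclusion.** The point holds in limited form. The visible target-selection rules do not exclude a previously irradiated, non-progressed lesion when other measurable disease exists, and the two time windows allow a target to be irradiated after its baseline measurement for about 14 days. In that sequence, shrinkage from radiotherapy can count towards PR or SD, so ORR and DCR can be overstated; the effect on mDOR is less certain because of the lower nadir. For lesions irradiated before the baseline scan, the direction is open.

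The size cannot be derived from the documents. The 0.4 to 8 point range at a true ORR of 20% rests wholly on assumed f (2% to 10%) and q (0.25 to 1). Nor do the documents show that ORR drives formal go/no-go decisions: they call the Simon design a guide and the aim preliminary efficacy. Confidence is moderate, given the redactions.

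**What to change.** Add a measurement rule to Appendix 11, sections 1.3/1.4, leaving all radiation intervals as they are:

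- A lesion in a previously irradiated or otherwise locally treated field may be a target only if clear progression after that treatment is documented by the baseline scan. Otherwise it is recorded as non-target.
- A lesion irradiated between the baseline scan and first dose is recorded as non-target.

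If targets have already been chosen, add to the SAP, which section 10.3 says is finalized before database lock, a sensitivity analysis of ORR and DCR that does not count responses or disease control relying on such lesions. It needs the field and dates of earlier radiotherapy matched to target lesions.

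The cost is a few sentences of text, with two consequences to accept. Some participants will have one target lesion fewer. And under Table 5 of Appendix 11, an irradiated lesion that persists as non-target caps the overall response at PR, so a CR cannot be recorded while it remains.
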